6.2.3. Medical History

Medical history will be recorded at screening and will be reviewed at baseline to ensure no changes have occurred since the screening visit. Clinically relevant findings that are present prior to study drug initiation must be recorded on the Medical History page in the eCRF. Clinically relevant findings found after study drug initiation and meeting the definition of an AE (new AE or worsening of previously existing condition) must be recorded on the AE page in the eCRF.

FSHD-specific history will be recorded at screening or at a subject's next scheduled study visit, if not previously recorded.

6.2.4. Vital Signs

Vital sign (pulse rate, respiration rate, blood pressure, and temperature) assessments will be performed at the time points specified in Table 2 and Table 3. Assessments will be taken after the subject has been seated or recumbent for at least 5 minutes and before any 12-lead ECG assessment or blood sampling is performed.

6.2.5. Physical Examinations

Physical examinations will be performed at the time points specified in Table 2 and Table 3.

Physical examinations at the screening visit and the safety follow-up visit will include an evaluation of body systems, including but not limited to the following: skin; head, eyes, ears, nose, and throat; respiratory system; cardiovascular system; abdomen (liver, spleen); lymph nodes; neurological system; and MSK system.

Symptom-directed physical examinations can occur at any time during the study if triggered by AEs or if deemed necessary by the investigator.

Weight (kg) will be recorded at screening and throughout the study at the time points specified in Table 2 and Table 3.

Height (cm) will be recorded and body mass index (BMI) calculated at screening and once yearly during the OLE: $BMI \text{ (kg/m}^2\text{)} = \text{weight (kg)} / (\text{height [cm]} / 100)^2$. Weight and height will be measured with shoes off and preferably with the same balance at each visit.

6.2.6. Twelve-Lead Electrocardiograms

Twelve-lead ECGs will be performed at the time points specified in Table 2 and Table 3. The primary ECG tracings will be locally read by the investigator. Any ECGs found to have abnormalities will be referred for a second opinion by a central reader.

Twelve-lead ECGs will be performed after subjects have been recumbent for at least 5 minutes. The ECGs should be performed after the measurement of vital signs and before any procedures that may affect heart rate (eg, blood sampling).

At the screening visit, if QTcF exceeds 450 msec for males or 470 msec for females, the ECG will be repeated 2 more times, and the average of the 3 QTcF values will be used to determine the subject's eligibility for the study.

Any clinically significant changes from baseline should be reported as AEs or SAEs, if applicable.

6.3. PHARMACOKINETIC AND PHARMACODYNAMIC ASSESSMENTS

6.3.1. Pharmacokinetic Assessments

During the placebo-controlled treatment period, blood samples will be collected to measure the plasma concentrations of losmapimod at Day 1 (baseline), Week 4, Week 16, and Week 36 at the

following time points: immediately predose and 4 hours (± 30 minutes) after administration of the study dose. Blood samples will also be taken, when feasible, after dosing during the Week 12, Week 24, and Week 48 visits, preferably ≥ 1 hour after dosing (Table 2). During the OLE, blood samples will be collected to measure the plasma concentration of losmapimod after dosing at the Week 144 visit, preferably ≥ 1 hour after dosing (Table 3).

For each plasma PK sample, approximately 3 mL of blood will be collected via an intravenous catheter placed in an antecubital vein in the arm into a 3 mL, lavender-capped vacutainer tube containing K2-EDTA. The indwelling catheter will be kept patent by saline flush after each blood sampling. The exact actual clock time of withdrawal of the blood sample will be recorded.

Skeletal muscle biopsies will be taken at Day 1 (baseline; predose) and at Week 16 or Week 36 to assess the losmapimod concentrations in muscle during the placebo-controlled treatment period (Table 2). Skeletal muscle biopsy procedures are described in Section 6.1.1.

Further detailed handling, processing, storage, and shipping procedures for plasma and skeletal muscle biopsy PK samples are described in laboratory manuals.

6.3.2. Pharmacodynamic Assessments

During the placebo-controlled treatment period, samples for assessing the target engagement estimates of losmapimod in peripheral blood will be collected at Day 1 (baseline) and Week 16 or Week 36 if it was not possible to collect the sample due to the COVID-19 pandemic, at the following time points: immediately predose and 4 hours (± 30 minutes) after taking the study dose (Table 2).

For drug target engagement measurements in skeletal muscle tissue during the placebo-controlled treatment period, each biopsy will be analyzed for pHSP27/total HSP27. Target engagement estimates of losmapimod in skeletal muscle biopsy will be taken at Day 1 (baseline; predose) and at Week 16 or Week 36 (Table 2). Skeletal muscle biopsy procedures are described in Section 6.1.1. Target engagement in muscle will be compared to target engagement in blood collected on the same day.

Further detailed handling, processing, storage, and shipping procedures for target engagement samples are described in a laboratory manual.

6.4. OTHER ASSESSMENTS

6.4.1. Reachable Workspace

The RWS Microsoft Kinect-based movement sensor system will be used at the visits noted in Table 2 to determine the subjects' RWS.

The RWS is a 3D sensor-based system (using a single depth-ranging sensor) that can unobtrusively detect an individual's RWS and reflects individual global upper extremity function, including shoulder and proximal arm. Previous and ongoing evaluation of the hardware

and software system using a commercially available and cost-effective single sensor platform (Microsoft Kinect sensor) has demonstrated its high reliability, repeatability, face validity, feasibility, sensitivity to change, and promise as a COA for FSHD and other neuromuscular disorders (Han et al, 2015).

During the evaluation, subjects will be seated in front of the Microsoft Kinect sensor and will undergo a standardized upper extremity movement protocol under the supervision of a study clinical evaluator while looking at a TV monitor. The evaluation will be performed with and without weights and on both the right and left arms. The Kinect sensor will track the 3D upper limb trajectory and transform the movements into a body-centric coordinate system. Each individual's RWS envelope will be reconstructed in a graphical output. Each side's RWS envelope will be divided into 4 quadrants, with the shoulder joint serving as the origin. The absolute total RWS surface envelope area (m^2) as well as areas for each of the quadrants will be calculated. Scaling of the data by each person's arm length will allow normalization for comparison between subjects (Han et al, 2015). RWS includes the functional workspace, where patients are instructed to touch certain parts of their body and are rated on their ability to complete this task.

Instructions for equipment assembly, setup, testing, and site certification; a manual of operation; and a quick reference guide will be described in a RWS manual. A central reader will be responsible for training, quality control, data analysis, and standardization of the RWS across all sites in the study.

6.4.2. Timed Up and Go

The classic and FSHD TUG test will be performed at the visits noted in Table 2.

The TUG test is a simple test that is used to assess a person's mobility and requires both static and dynamic balance. It measures the time that a person takes to rise from a chair, walk 3 meters, turn around, walk back to the chair, and sit down. The optimized TUG test is the classic TUG but adds the component of getting up from a laying position on a bed-like table in the clinic at the start of the test and laying back down on his or her back at the end of the test. The test will be done twice per visit.

A manual of operation, traditional TUG source documents, and FSHD TUG source document will be described in a TUG manual. A central reader will be responsible for training, quality control, data analysis, and standardization of the TUG and FSHD TUG across all sites in the study.

6.4.3. Dynamometry

Dynamometry will be performed at the visits noted in Table 2.

Quantitative isometric dynamometry (hand-held dynamometer) will be used to assess the skeletal muscle strength of study subjects in both the upper and lower limbs bilaterally. Shoulders, flexors and extensors in the elbow, knees, and ankles as well as the grip will be measured at each

applicable visit. Isometric dynamometry measures the static muscle strength without any movement.

Further details of the assessment will be provided in a study reference manual. All sites will use the same equipment and standardized testing procedure.

6.4.4. Motor Function Measure Domain 1

The MFM scale Domain 1 assessment will be performed at the visits noted in Table 2.

The MFM scale assesses the severity of the motor deficit as determined by an experienced physical therapist (Bérard et al, 2005). The score is reproducible, the coefficients of the interrater reliability are good or excellent. Domain 1 of the MFM provides a clinician's assessment of functional impairment for standing and transfers.

Instructions for performing the MFM scale Domain 1 assessment will be provided in a study reference manual.

6.4.5. FSHD Health Index

The FSHD-HI will be performed at the visits noted in Table 2.

The FSHD-HI is an FSHD-specific patient-reported measure of disease burden on activities of daily living, quality of life, and symptom prevalence and severity. It consists of a questionnaire with 116 items developed from qualitative interviews of patients followed by a national cross-sectional validation study. The measure consists of 14 subscales that measure a patient's perception of their ambulation and mobility, hand function, shoulder and arm function, emotional health, back/chest/abdomen strength, fatigue, pain, eating function, ability to do activities, communication ability, satisfaction in social situations, performance in social situations, body image and cognition. Scoring is performed centrally by the developer.

6.4.6. Patients' Global Impression of Change

The PGIC will be performed at the visits noted in Table 2 to obtain the subjects' rating of overall improvement.

6.4.7. Genetic Confirmation of FSHD1

[figure not shown]
Genetic testing for FSHD1 is highly sensitive and specific. The finding of a D4Z4 contraction on chromosome 4q35 likely has a sensitivity of 93% and a specificity of 98% for the diagnosis of clinically defined FSHD. Healthy individuals possess at least 11 D4Z4 repeats, yielding a DNA fragment >38 kb on standard genetic testing. Affected individuals possess between 1 and 10 repeats, yielding DNA fragments ranging from 10 to 38 kb in size. Measurement of the size of the residual D4Z4 sequence on 4q35 forms the basis for genetic testing in FSHD (Tawil et al, 2015). For this study, only subjects with 1 to 9 repeats will be enrolled. The number of repeats will be calculated by a diagnostic laboratory using the size of the D4Z4 bands on Southern blot testing. The site will enter the number of repeats into the IRT system. Subjects with 10 repeats

will be excluded from the study because such individuals tend to have slower progression and are more variable due to the presence of genetic modifiers.

Genetic confirmation must be obtained before the subject is randomized and before the baseline muscle biopsy is performed. Genetic confirmation can come from previous testing, if verified with appropriate documentation from an accredited laboratory. If genetic testing is necessary, the 4-week screening window and activities will not start until the results are obtained and verified by the principal investigator.

Due to the stable transmission of repeat sizes within families, subjects with a clinical diagnosis of FSHD who have a first-degree relative with a genetically confirmed diagnosis of FSHD1 may be entered into the study for screening assessments including MRI. During screening, a confirmatory genetic diagnosis will be conducted. If genetic testing during screening is necessary, the 4-week screening window will not start until the results are obtained and verified by the principal investigator.

Further detailed handling, processing, storage, and shipping procedures for genetic testing samples are described in a laboratory manual.

6.5. SAFETY REVIEW COMMITTEE

As detailed in Section 11.1.1, a safety review committee (SRC) will review safety data from the study.

6.6. PREGNANCY

Pregnancy is not regarded as an AE unless there is a suspicion that the study drug may have interfered with the effectiveness of a contraceptive medication. Any pregnancy that occurs during study participation must be reported as an SAE. Study staff should complete the paper Pregnancy Initial Report Form and fax the form to [REDACTED] Pharmacovigilance within 24 hours of awareness or call the [REDACTED] safety hotline to report. To ensure subject safety, irrespective of the treatment received by the subject, any pregnancy occurring during study drug administration or until follow-up must be reported within 24 hours of the investigator's knowledge of the event to the sponsor.

If a woman becomes pregnant while on study drug, the study drug must be discontinued immediately. The investigator must counsel the subject and discuss the potential risks to the pregnancy and the possible effects on the embryo or fetus. The pregnancy must be followed up to determine the outcome (including spontaneous miscarriage, elective termination, normal birth, or congenital abnormality) and status of mother and child, even if the subject was discontinued from the study. Pregnancy complications and elective terminations for medical reasons must be reported as an AE or SAE. Spontaneous miscarriages must be reported as an SAE.

Any SAE occurring in association with a pregnancy that is brought to the investigator's attention after the subject has completed the study and considered by the investigator as possibly related to the study drug must be promptly reported to [REDACTED] and Fulcrum Therapeutics.

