6.2.1.6. Reporting Serious Adverse Events

The investigator must report any AE that meets the SAE criteria (Section 6.2.1.2) to [REDACTED] immediately (ie, within 24 hours after the site personnel first learn about the event) via electronic data capture (EDC). In the event that EDC entry is not possible (eg, system failure or access problems), the study site staff should complete the paper SAE report form and fax the form to [REDACTED] Pharmacovigilance within 24 hours of awareness or call the [REDACTED] safety hotline to report. The study site staff should update the EDC system as soon as it is available.

A full description of every SAE will need to be provided to [REDACTED] Pharmacovigilance. The following contact information should be used if reporting SAEs via fax or phone:

Pharmacovigilance

US:

Rest of world:

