7.1.2. Secondary Endpoints

The secondary endpoints of the placebo-controlled treatment period are as follows:

- Safety and tolerability of losmapimod as defined by the following:
 - Type, frequency, severity, seriousness, and relationship of AEs to losmapimod
 - Incidence of AESIs
 - Number of subjects who prematurely discontinue study drug due to an AE
 - Frequency of clinically significant changes in laboratory test, ECG, vital sign, and physical examination results
- Change from baseline in MFF, LMV, and MFI at Week 12, Week 24 (if applicable) and Week 48
- Plasma concentrations of losmapimod at Week 4, Week 12, Week 16, Week 24, Week 36, and Week 48
- Concentrations of losmapimod in skeletal muscle biopsy at steady state at Week 16 or Week 36
- Target engagement parameters in blood, and skeletal muscle biopsy at Week 16 or Week 36

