### **9.1.4. Serious TEAEs**

The seriousness of an AE should be assessed independently by the Investigator. An SAE is defined as any untoward medical occurrence that at any dose results in death, is life-threatening, is a congenital anomaly/birth defect, requires in-patient hospitalization or prolongation, or results in significant disability.

Important medical events that may not result in death, be life-threatening, or require hospitalization may be considered SAEs when, based upon medical judgment, they may jeopardize the subject and may require medical or surgical intervention to prevent one of the outcomes listed above.

SAE data will be presented by SOC and PT in the same manner as described in [Section 9.1.1](#).

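### Protocol 6.6 says a pregnancy is not an AE unless contraceptive interference is suspected, then orders every pregnancy reported as an SAE, so an uncomplicated pregnancy could be counted in the serious TEAE tables

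*Protocol*

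**What the plan says.** Protocol 6.6 opens with "Pregnancy is not regarded as an AE unless there is a suspicion that the study drug may have interfered"; the interference in question is with how well a contraceptive works. The next sentence reads "Any pregnancy that occurs during study participation must be reported as an SAE", with no condition attached. The one after that gives a dedicated route: "Study staff should complete the paper Pregnancy Initial Report Form", sent by fax or telephoned in, with a 24-hour limit.

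The second paragraph of 6.6 gives separate rules for particular outcomes. Complications and terminations for medical reasons are an AE or an SAE. For miscarriage the rule is "Spontaneous miscarriages must be reported as an SAE". The same paragraph stops study drug when a woman on treatment becomes pregnant, and a footnote to Table 2 ends her participation in the study.

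Elsewhere, protocol 6.2.1.2 lists what makes an event serious, and SAP 9.1.4 repeats the list: "An SAE is defined as any untoward medical occurrence that at any dose results in death, is life-threatening", followed by the remaining outcomes. Protocol 7.1.2 includes among the controlled-period safety endpoints "Number of subjects who prematurely discontinue study drug due to an AE". Protocol 4.2.1 gives pregnancy as an example in its residual category of withdrawal reasons (item 7), apart from the item for serious or intolerable AEs (item 3).

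**The concern.** An SAE is a subset of the AEs, because protocol 6.2.1.6 applies the seriousness criteria to AEs. An event that is not an AE therefore cannot be an SAE. A site facing an uncomplicated pregnancy without suspected contraceptive interference has two instructions and can follow only one.

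Safety based on AEs is the primary endpoint of the OLE (protocol 7.2.1, SAP 3.2.1). If a site follows the second sentence, an event that is not toxicity is recorded as serious. If sites differ in which sentence they follow, the SAE count depends partly on the site. The serious TEAE tables 14.3.2.1.1 and 14.3.2.1.2 are marked for the Safety Review Committee (SRC), and SAP Section 12 lets that committee meet ad hoc on SAE rates, so a misclassified event could also affect monitoring.

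**Working it through.** The plan gives no figure on this point, so the check is mainly a comparison of texts.

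1. **Where the two sentences conflict.** With suspected contraceptive interference, pregnancy is an AE under the first sentence and an SAE under the second, so the first does not rule out the second. Without it, the first says not an AE and the second says SAE. The conflict covers only this second group.

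2. **Seriousness criteria.** Protocol 6.2.1.2 and SAP 9.1.4 name death, threat to life, hospitalization, disability and congenital anomaly, plus important medical events. Pregnancy is not named, and an uncomplicated one meets none of these.

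3. **Internal evidence in 6.6.** If every pregnancy were already an SAE, the miscarriage rule would be redundant and the rule for complications and medical terminations largely so. The rest of the section fits the first sentence better.

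4. **Path into the tables.** SAP 9.1 defines a TEAE by onset relative to dosing, and SAP 9.1.4 leaves seriousness to the investigator. An on-treatment pregnancy recorded as an SAE would therefore enter 14.3.2.1.x. SAP 9.1 to 9.1.7 contain no pregnancy rule. SAP 9.1 also treats a missing causality assessment as drug-related, so a pregnancy SAE with that field blank would appear in the overview as a drug-related serious TEAE.

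5. **Treatment discontinuation.** 6.6 stops study drug, and SAP 9.1.5 tabulates TEAEs that caused this. Protocol 4.2.1 classes pregnancy apart from AEs, but its list concerns withdrawal from the study. How the reason for stopping study drug is coded is left open.

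6. **Scale in the OLE tables.** The tables use the Open-label Analysis Set, shown in four groups by treatment sequence and entry point (SAP 4.2), with a total column for OLE TEAEs (SAP 9.1).
   - Total column: at most the 80 enrolled, so one event adds at least 1/80 = 1.25 percentage points.
   - Week 24 rollover: 12 subjects across two columns (protocol 3.1.1). Neither column can exceed 12, so one event adds at least 1/12 = 8.3 points in its column.

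7. **Frequency.** The documents give no number of pregnancies and no number of women of child-bearing potential. Protocol 5.5.1 requires methods with a failure rate below 1% per year when used correctly. Even if all 80 subjects were such women, the expected number would be under 80 × 0.01 = 0.8 per year. The true number at risk is smaller, since men were eligible, but the OLE has no fixed end date.

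**The case against.** The best defence is that the disputed sentence only sets the reporting speed. The sentence after it sends staff to a pregnancy form, whereas 6.2.1.6 uses electronic data capture, with a paper SAE form as backup. That reading is possible, so the text supports only that a pregnancy could be counted as an SAE, not that it would be. It does not remove the contradiction: the sentence says what the event is to be reported as, and the 24-hour limit is stated separately.

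A second defence is that the SAP screens such events out, because a TEAE must first be an AE and an SAE must be an untoward occurrence with a listed outcome. This has some force as a matter of definition. But the SAP describes no step that re-tests a recorded SAE against the definition, and the investigator who decides seriousness is the person 6.6 instructs.

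Two stronger readings are tempting:

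- **Automatic counting as an AE discontinuation.** A reader might infer this because 6.6 stops study drug. The documents do not say so, and 4.2.1 points the other way for study withdrawal. It remains a coding risk.
- **A distortion of 1/40 = 2.5 points per randomized arm.** A reader might infer this from an even split of 80. It does not describe the OLE tables. Their analysis set requires completing 24 or 48 weeks of controlled treatment and taking an OLE dose, and the Table 2 footnote ends participation when pregnancy is found. A pregnancy found before rollover should therefore not reach them. They would mainly capture OLE pregnancies, when everyone takes losmapimod. The controlled period has its own SAP, which is not among the documents, so its handling cannot be checked.

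The rarity argument stands. Few events are expected, possibly none.

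**Conclusion.** Section 6.6 is wrong as written. Its first two sentences cannot both be followed for a pregnancy without suspected contraceptive interference, and the second conflicts with the seriousness criteria in both documents. The consequence is conditional: an uncomplicated pregnancy could be recorded as an SAE and counted in the serious TEAE tables, and no pregnancy-specific rule in the OLE SAP prevents it. Double counting as an AE discontinuation is possible but not stated.

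The minimum effects of 1.25 points (total column) and 8.3 points (a Week 24 rollover column) assume one event in the largest possible denominator. How often this would happen is unknown. No efficacy conclusion is affected. The correction is worth making because it concerns the OLE primary safety endpoint and costs very little.

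**What to change.** **Protocol.** Reconcile the first two sentences of 6.6 with each other and with 6.2.1.2 and 4.2.1. The revision should keep:

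- the 24-hour notification on the pregnancy form and the outcome follow-up;
- the exception for suspected contraceptive interference, which a blanket statement that pregnancy is never an AE would override;
- the AE and SAE rules for complications, medical terminations and miscarriages.

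**SAP 9.1 and 9.1.4.** List pregnancies and their outcomes separately. State that a pregnancy that is not an AE under the reconciled 6.6 does not enter the serious TEAE tables (14.3.2.1.x) or the tables of TEAEs leading to treatment discontinuation (14.3.1.5.x). The controlled-period SAP should be checked for the same rule.

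**Cost.** About one sentence in the protocol and one in the SAP, plus a pregnancy listing. No safety information is lost, because notification, follow-up and the interference exception all stay.
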